#### Sample size

Sample size was calculated based on online openepi calculator. We calculated the required sample size to detect a statistically significant difference in AE rates between groups using a two-sided chi-square test. Therefore, our planned enrollment of 80 patients (40 per group) is sufficient to detect clinically meaningful differences in treatment-emergent adverse events.

#### Inclusion criteria

Eligible trial participants will be women who have

1. Pathologically confirmed invasive breast ductal carcinoma
2. Hormone receptor negative (<1% positive cells by immunohistochemistry staining) and ERBB2 negative.
3. Participants had early-stage tumors that were stage T1b-3N0-3cM0, without positive supraclavicular or internal mammary lymph node involvement based on the American Joint Committee on Cancer (AJCC 2010, seventh edition) staging criteria.
4. They received standard treatments, including modified radical mastectomy or breast-conserving surgery, neo-/adjuvant chemotherapy, and radiotherapy according to institutional guidelines.

#### Exclusion criteria

Key exclusion criteria will include

1. Inflammatory or bilateral breast cancer.
2. History of invasive breast cancer or other malignancies; receipt of other biologic agents or immunotherapy.
3. Lactation or pregnancy; or severe coexisting illness.

#### Study end points

The primary end point of the study is to assess the adverse effects of the Capecitabine after 6 months after starting treatment.

Secondary end points will include

1. Disease-free survival, defined as the time from randomization to the first occurrence of the following events: local relapse, distant metastasis or contralateral breast cancer.
2. overall survival (the time from randomization to death from any cause).
3. Adverse events were assessed and graded according to the National Cancer Institute's Common Terminology Criteria for Adverse Events version 4.0. Hand-foot syndrome (a common adverse effect of the fluoropyrimidine chemotherapy agent capecitabine) events will graded from 1 to 3.

Statistical Analysis:

For statistical analysis, all data will recorded and analyzed .The p-value reports will two tailed and an alpha level of 0.05 was used to assess statistical significance. Time-to-event curves will be described using the Kaplan-Meier method. A Cox proportional hazards model will be used to estimate and test the treatment effect. Analysis of the interaction between treatment effects and selected subgroups will conducted using a  $\chi^2$  test for heterogeneity and described with forest plots. Q statistics and I values will be used to assess the potential heterogeneity of trial-specific Disease-Free Survival. The data will be coded and entered using: the statistical package for social science version 22 (SPSS v 22). For descriptive analysis of the result, the data will be summarized using (minimum, maximum, mean and standard deviation) for quantitative data and the frequency distribution for qualitative data. Student t- test: for comparison between means of two groups of quantitative variables. Paired sample t-test will be used for comparison between means of paired quantitative variables. Chi square test: for comparison between two groups of categorical data or frequency of events.

P: The probability/significance value

P value  $\geq 0.05$ : Not significant

P value  $< 0.05$ : Significant

The Correlation coefficient (r): A positive correlation coefficient means that as the value of one variable increases, the value of the other variable increases; as one decreases the other decreases. A negative correlation coefficient indicates that as one variable increases, the other decreases, and vice-versa. Graphic presentations in this study will done by: means of "Microsoft excel version 2007".

Ethical considerations:

This study will be approved by faculty of Medicine; Beni-Suef university research Ethics committee (FBBSU-REC)which adhered to principles of the Declaration of Helsinki. Informed consents will be signed from the participants, after explanation of the study to all participants.

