## Methods

Eligible patients will randomly open label assigned in a 1:1 ratio to receive either low-dose capecitabine maintenance (intervention group) which is newly diagnostic to be planned to receive capecitabine after finishing the standard adjuvant treatment or observation (control group) within 4 weeks after completion of standard adjuvant chemotherapy.

The capecitabine maintenance group will receive oral capecitabine at 650 mg/m^2, twice daily continuously for 1 year.

Total follow up of the study is 2 years, one year for drug receiving with monthly follow up for adverse effect and the other year for every 3 months follow up to assess DFS and OS.

Collection of capecitabine dose will receive and adverse events will be assessed monthly during capecitabine maintenance in the capecitabine group. In both groups, physical examination, assessment of menopausal status, breast ultrasound, and abdominal ultrasound were performed every 3 months during 2 years of follow up; mammography and chest x-ray were performed yearly. Patients who have not experienced recurrence or death at the time of data analysis will be censored as alive and event-free at the date of last follow-up.

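### The disease-free survival definition leaves out death, while the censoring rule in Methods implies that death is an event

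*Combined protocol and SAP*

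**What the plan says.** Study end points lists DFS as the first secondary end point, timed from randomization to the "first occurrence of the following events: local relapse, distant metastasis or contralateral breast cancer". Death is named only in the next item, "overall survival (the time from randomization to death from any cause".

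Methods gives the plan's one censoring rule: "Patients who have not experienced recurrence or death at the time of data analysis will be censored as alive and event-free", with the censoring date set at last follow-up. The rule does not say which end point it serves.

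The Statistical Analysis text under Study end points says "Time-to-event curves will be described using the Kaplan-Meier method" and "A Cox proportional hazards model will be used to estimate and test the treatment effect". It names no method for competing risks. Nothing in the document says how a death without prior relapse is handled for DFS.

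**The concern.** The two sections treat a death without relapse differently. Under the end point definition it is not a DFS event. Under the Methods rule the patient is not in the group to be censored, which implies an event. The DFS event count, the Kaplan-Meier curve and the Cox estimate then depend on which section the analyst follows.

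An end point called disease-free survival would normally be read as one in which a patient who has died is no longer a disease-free survivor. Under the definition as written, such a death on either arm would not count against DFS. The trial is open label, and the coding could be settled after the deaths and their arms are known. A prespecified definition exists to prevent that.

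**Working it through.** **The two rules side by side**

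| Patient at analysis | DFS by Study end points | By the Methods censoring sentence |
|---|---|---|
| Alive, no relapse | no event | censored |
| Relapse, alive or later dead | event at relapse | not censored |
| Dead without relapse | no event | not censored, so by implication an event |

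Only the last row conflicts. A death after relapse changes nothing for DFS, because the relapse came first.

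The Methods sentence does not work as an OS rule. For OS, a living patient with a recurrence must be censored, and the sentence leaves that patient out. It suits an end point whose events are recurrence or death.

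**Inputs from the plan.** 40 per group (Sample size); 1:1 allocation and 2 years of follow-up (Methods); Kaplan-Meier and Cox (Statistical Analysis). The plan gives no DFS figure to reproduce: there is no DFS event rate or event target, and the sample size rests on adverse event rates. Relapse counts, death times and rates below are therefore assumptions.

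**Crude share.** One death without relapse in an arm of 40: 1/40 = 2.5 percentage points.

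**Kaplan-Meier at 2 years.** Take one arm of 40 with *r* relapses, one death without relapse after *j* of them, and everyone else followed to 24 months.

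- Death counted: S = (39 − r)/40
- Death censored: S = [(40 − j)/40] × [(39 − r)/(39 − j)]
- Difference: (39 − r)/[40 × (39 − j)]

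| r | Death before all relapses (j = 0) | Death after all relapses (j = r) |
|---|---|---|
| 0 | 39/1560 = 2.50 points | 2.50 points |
| 5 | 34/1560 = 2.18 points | 2.50 points |
| 8 | 31/1560 = 1.99 points | 2.50 points |

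For 0 to 8 relapses the shift is 2.0 to 2.5 points, whenever the death occurs.

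**Cox model, illustration only.** 40 per arm, the same *r* evenly spaced relapse times over 24 months in both arms, Efron ties, one death without relapse. With no such death the hazard ratio (capecitabine against observation) is 1.00 under both codings.

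| Arm of death | r per arm | Month of death | HR (95% CI), censored | HR (95% CI), counted |
|---|---|---|---|---|
| Capecitabine | 5 | 6 | 1.02 (0.30–3.53) | 1.22 (0.37–4.01) |
| Capecitabine | 8 | 6 | 1.02 (0.38–2.72) | 1.15 (0.44–2.98) |
| Observation | 5 | 6 | 0.98 (0.28–3.38) | 0.82 (0.25–2.68) |
| Observation | 8 | 6 | 0.98 (0.37–2.61) | 0.87 (0.34–2.26) |

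With the death at month 12, the ratios on capecitabine are 1.01 against 1.22 (r = 5) and 1.01 against 1.14 (r = 8). On observation they are 0.99 against 0.82 and 0.99 against 0.88. Moving the death to month 0.5 or 23.5 widens the ranges slightly: 1.00–1.03 against 1.12–1.23 on capecitabine, and 0.97–1.00 against 0.81–0.89 on observation. Every interval includes 1.

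**Several deaths, on assumed rates.** With constant hazards, a 2-year recurrence risk *p* and a 2-year risk *d* of death without recurrence, DFS is 1 − p with deaths censored and (1 − p)(1 − d) with deaths counted.

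- p = 10%: 0.900 against 0.9 × 0.99 = 0.891 (d = 1%) and 0.9 × 0.95 = 0.855 (d = 5%)
- p = 20%: 0.800 against 0.8 × 0.99 = 0.792 and 0.8 × 0.95 = 0.760

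Counting these deaths adds about 1 to 4 DFS events among 80 patients.

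**The case against.** The best reply is that there is a gap here but no contradiction. The Methods sentence says that patients without recurrence or death are censored; it does not say that only they are. It names no end point, and the same section says that follow-up serves both DFS and OS. It can be read as a joint description, event-free for DFS and alive for OS, with death belonging to OS alone. On that reading the sentence is merely incomplete.

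Part of this stands. Methods implies that death is an event and does not state it, so which definition the investigators intended cannot be settled from the text. That is why the relapse-only option has to stay open in the fix. But the joint reading does not remove the problem: the explicit definition still leaves death out of DFS, and the plan still does not say how a death without relapse enters the Kaplan-Meier and Cox analyses.

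The second reply concerns size. DFS is secondary, the primary end point is adverse effects at 6 months, patients with severe coexisting illness are excluded, and deaths without relapse may be few over 2 years. The hazard ratio shift partly reflects how few events are assumed, and no conclusion is shown to change. All of this is fair. It limits the weight of the point but does not remove it.

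**Conclusion.** The concern holds. The DFS definition is wrong as written for an end point of that name, and it does not agree with what the censoring rule implies. One death without relapse is worth 2.5 points of its arm, or 2.0 to 2.5 points of 2-year Kaplan-Meier DFS on the assumption of 0 to 8 relapses and complete follow-up. In the Cox illustration, with 5 to 8 relapses per arm and the death at month 6 or 12, counting it moves the hazard ratio from 1.01–1.02 to 1.14–1.22 if it is on capecitabine, and from 0.98–0.99 to 0.82–0.88 if on observation.

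The inconsistency itself rests on the text alone and is certain. Its practical size depends on how many such deaths occur, for which the plan gives no rate. No figure stated in the plan changes, and the deaths remain visible in OS. It should be fixed, but it does not threaten the primary analysis.

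**What to change.** 1. In Study end points, add death from any cause to the DFS events.
2. In Methods, confine the existing censoring sentence to DFS.
3. Add a sentence for OS: patients still alive are censored at last follow-up, whether or not they have relapsed.

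If the investigators want an end point based on relapse alone, they should give it a name that says so and state how a death without relapse is treated.

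The cost is two or three sentences of protocol wording. No new data are needed, since deaths are already required for OS. Only the relapse-only option could call for a method beyond the planned Kaplan-Meier and Cox analyses. The wording should be settled before any outcome data are examined by arm.

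### The primary end point names no single adverse-event variable and every P<0.05 is labelled significant, so 0.05 is not the error rate of the primary conclusion

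*Combined protocol and SAP*

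**What the plan says.** All references are to the Combined protocol and SAP.

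- **Primary end point (Study end points):** "The primary end point of the study is to assess the adverse effects of the Capecitabine after 6 months after starting treatment". No AE term, grade threshold, composite or per-patient summary follows.
- **Secondary end points (same section):** DFS, OS, and AEs again: "Adverse events were assessed and graded according to the National Cancer Institute's Common Terminology Criteria for Adverse Events version 4.0". Hand-foot syndrome is the only event named.
- **Significance rule (Statistical Analysis, under Study end points):** "The p-value reports will two tailed", then "an alpha level of 0.05 was used to assess statistical significance", and as a general legend "P value $< 0.05$ : Significant". There is no hierarchy, alpha split or adjustment, and no test is called exploratory.
- **Tests (same text):** chi-square for event frequencies, a Cox model to test the treatment effect, and interaction tests in an unstated number of unnamed subgroups.
- **Sample size:** "We calculated the required sample size to detect a statistically significant difference in AE rates between groups using a two-sided chi-square test". The total is 80 patients, 40 per group. The section gives no AE, no rates and no power.
- **Methods:** monthly AE assessment is scheduled explicitly only for the capecitabine group. The schedule for both groups lists examination, menopausal status and imaging, but not AEs.

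**The concern.** Safety tables are usually left unadjusted because some other end point decides the trial. Here AEs are the primary end point and the basis of the sample size, yet no rule says which AE result is decisive. Primary and secondary AE results cannot be told apart. Someone following the plan could take any AE comparison with P<0.05 as the primary finding after seeing the data.

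The same label would attach to a DFS, OS or subgroup P value. The Introduction and Aim of the work describe the study as an evaluation of efficacy too, so such a result would be read as an efficacy claim from a trial sized only on AEs.

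**Working it through.** **Inputs from the document:** 0.05 per test, two-sided; 40 per group; chi-square for AEs; Cox tests for DFS and OS; subgroup tests in the plural.

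**Assumptions, because the document is silent:** number of AE terms, AE rates, correlation between tests, and whether the chi-square test is continuity-corrected (Yates). All error rates below are for true null comparisons.

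**Step 1. The plan's own figure.** The 80 patients can be neither reproduced nor refuted, because rates and power are missing. Using n per group = [1.96·sqrt(2p̄(1−p̄)) + z_β·sqrt(p1(1−p1) + p2(1−p2))]² / (p1−p2)², 40 per group gives 80% power for about:
- 5% v 28%, 10% v 36% or 20% v 49.5% without continuity correction;
- 5% v 31.5%, 10% v 39% or 20% v 52.5% with it.

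So the size may suit one AE variable, but the document does not say which.

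**Step 2. Smallest sets of tests, independent.** Chance of at least one false significant label = 1 − 0.95^k.
- k=1: 5.0%.
- k=3 (one AE measure, DFS, OS): 1 − 0.8574 = 14.3%.
- k=5 (adding two subgroup tests, the fewest a plural implies): 1 − 0.7738 = 22.6%.

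**Step 3. The same sets, correlated.** Equicorrelated normal statistics, 200,000 simulated draws, counting max|Z| > 1.96.
- k=3: 12.6% at correlation 0.5; 11.0% at 0.7.
- k=5: 18.1% at 0.5; 14.9% at 0.7.

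**Step 4. The AE family alone, 10 terms (assumed count), independent.** The formula in Step 2 takes each test to have size exactly 0.05, but a 40 v 40 chi-square test on uncommon events does not. The exact size at a common rate p is the sum, over all counts x and y from 0 to 40, of Bin(x; 40, p)·Bin(y; 40, p) wherever |z| > 1.96. Here z = (|x−y|/40) / sqrt(p̄(1−p̄)·2/40), and Yates subtracts 1/40 from the numerator. The family rate is 1 − (1 − size)^10.

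| AE rate, both arms | Size, uncorrected | 10 terms | Size, Yates | 10 terms |
|---|---|---|---|---|
| 2% | 0.0074 | 7% | 0.0001 | 0.1% |
| 5% | 0.0434 | 36% | 0.0040 | 3.9% |
| 10% | 0.0587 | 45% | 0.0137 | 13% |
| 20% | 0.0511 | 41% | 0.0222 | 20% |
| Mixed, 5–50% | varies | 41% | varies | 17% |

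**Step 5. Adding DFS and OS to the 10 terms** (independent, each of size 0.05).
- Mixed rates, uncorrected: 1 − (1 − 0.413)·0.95² = 47%.
- Mixed rates, Yates: 1 − (1 − 0.168)·0.95² = 25%.
- All at 5%, Yates: 1 − (1 − 0.0389)·0.95² = 13.3%.

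**The case against.** **Per-term testing is not stated.** A reader might infer that every AE term will be tested. The document gives a generic chi-square rule and a generic P-value legend. Testing each term is an inference from the plural end point. This stands, and it is why the 10-term figures are conditional.

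**No stated figure is contradicted.** A reader might take 0.05 as a promised trial-wide rate that the plan breaks. The plan never calls it trial-wide. What is missing is a rule that identifies the decisive test.

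**Inflation is not always large.** A reader might conclude that the false-positive rate is far above 5% whatever the inputs. With rare events and Yates correction, the AE family alone falls below 5%.

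**The global null is unlikely.** Capecitabine is compared with no treatment, and the plan itself calls hand-foot syndrome common with this drug. The rates therefore apply only to comparisons that are truly null. A false AE signal also overstates toxicity, whereas missed harm is the more usual worry. Both points are fair. They limit the harm but do not say which comparison is primary.

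**DFS and OS are already secondary in a phase 2 trial.** Formal adjustment there is not essential. That stands, but the plan still gives their P values the same label as the primary result and does not call them exploratory. It gives no event rate, so nothing firm can be said about how few events there will be.

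**Comparative AE data may not exist.** Methods does not schedule AE assessment in the observation group. This is a real conflict with the test in Sample size, and any fix has to settle it.

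**Conclusion.** The point holds as a defect in the decision rule. An unnamed primary variable, AEs listed at two levels and one blanket significance label leave the choice of decisive test open, so the stated 0.05 does not describe the error rate of the primary conclusion.

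For the smallest plausible set (one AE measure, DFS and OS), the chance of at least one false significant label is about 11–14%. This needs no assumption about the number of AE terms, but it takes each test at its nominal size. It is the rate for the whole set of labels, not for the primary test alone. For the AE family, the range from 0.1% to 45% in the cases checked rests on an assumed 10 independent terms, assumed rates and the choice of correction. It shows that the error rate is uncontrolled, not that it takes a particular value.

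The documents do not support a claim that 80 patients is wrong, or that safety terms must be adjusted for multiplicity. The change is worth making before analysis.

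**What to change.** 1. In Study end points, name one patient-level primary AE variable. An example is the proportion of patients with at least one AE at or above a pre-stated CTCAE v4.0 grade by 6 months from randomization. Counting from randomization gives the observation group a start date, which counting from the start of treatment does not.
2. Test only that variable at two-sided 0.05, say whether the chi-square test is continuity-corrected, and limit the significance label to that test.
3. Tie the Sample size calculation to it, stating the assumed rates and power.
4. Report other AE terms, DFS, OS and subgroup interactions as exploratory estimates with 95% confidence intervals.
5. Reconcile the AE schedule in Methods with the between-group test in Sample size, so that the primary variable is recorded in the same way in both arms.

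Splitting alpha instead would cost power. At 0.05/10 = 0.005 with 40 per group, power for 20% v 50% falls from 82% to 50%, and for 5% v 30% from 85% to 56% (assumed rates). Naming one variable avoids that.

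Items 1 to 4 need wording only. Item 5 may add AE recording in the observation group if none is planned. The downside is that secondary and individual AE results can no longer be called significant.

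### The Cox model for DFS and OS names no covariate or stratum and allocation is unstratified, so a chance nodal imbalance between two groups of 40 would shift the hazard ratio; stratifying by node status removes this cheaply

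*Combined protocol and SAP*

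**What the plan says.** The Statistical Analysis text, under Study end points, covers the treatment comparison for DFS and OS in one sentence: "A Cox proportional hazards model will be used to estimate and test the treatment effect". No covariate, stratum or adjusted sensitivity analysis follows. Significance is judged "two tailed and an alpha level of 0.05 was used to assess statistical significance". A heterogeneity test across unnamed subgroups is also planned, but it does not adjust the main treatment effect.

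Under Methods, patients are "randomly open label assigned in a 1:1 ratio". No stratification factor, blocking or minimisation is mentioned.

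Under Inclusion criteria, the population is "stage T1b-3N0-3cM0, without positive supraclavicular or internal mammary lymph node involvement". Prior chemotherapy may have been neoadjuvant or adjuvant.

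DFS and OS are secondary. The primary end point is adverse effects at 6 months, and the sample size rests on it: "our planned enrollment of 80 patients (40 per group) is sufficient to detect clinically meaningful differences in treatment-emergent adverse events".

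**The concern.** Nodal stage is a natural candidate for a prognostic factor, and the eligibility criterion is written in terms of it, so it has to be established for every patient before entry. Yet neither the allocation nor the named analysis uses it. With 40 patients per arm, simple randomisation can leave one arm with noticeably more node-positive patients. If node-positive patients relapse sooner, a treatment-only hazard ratio moves in the direction of that imbalance and part of what is reported as a capecitabine effect is a nodal effect.

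The silence matters for a second reason. The trial is open label, so a decision about adjustment taken at analysis could be made with both the imbalance and its effect on the hazard ratio in view.

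**Working it through.** **Inputs from the documents.** 40 per group; 1:1 allocation without stratification; two-sided alpha 0.05; two years of follow-up; N0 to N3c, limited by the node-site clause.

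**Inputs that are assumptions.** Node-positive share p = 30-50%; nodal HR h = 2-3; two-year event risk 10-30%. The Study design section describes the patients as low risk, so the real nodal spread may be narrower than the eligibility criterion allows; those two passages should be reconciled.

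**The plan's own figure.** The 40 per group cannot be reproduced, because no adverse-event rates, difference or power are given. At 80% power without continuity correction it would fit, for example, 10% vs 36% or 20% vs 49%. It says nothing about DFS.

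**Step 1: how often imbalance occurs.** The SD of the between-arm difference is √(2p(1−p)/40). At p = 0.4 this is √(0.48/40) = 0.110, or 11 points. The probabilities below come from two independent binomials of size 40 and count both directions.

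| Node-positive share | ≥10 points (4 patients) | ≥15 points (6) | ≥20 points (8) |
|---|---|---|---|
| 30% | 39% | 18% | 6.7% |
| 40% | 42% | 21% | 8.6% |
| 50% | 43% | 22% | 9.3% |

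By symmetry, a 20-point excess in one particular arm has half the last column: 3.3%, 4.3% and 4.7%.

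**Step 2: size of the shift when the true treatment HR is 1.** With an excess d in the capecitabine arm, the approximate treatment-only HR is [1 + (h−1)(p + d/2)] / [1 + (h−1)(p − d/2)].
- d = 0.20, h = 2, p = 0.5: 1.6/1.4 = 1.14.
- d = 0.20, h = 3, p = 0.3: 1.8/1.4 = 1.29.
- Across p = 0.3-0.5 and h = 2-3: 1.07-1.13 at 10 points, 1.11-1.21 at 15 points and 1.14-1.29 at 20 points.

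An excess in the control arm gives the reciprocals. The rounded range 1.1-1.3 becomes 1/1.3 = 0.77 to 1/1.1 = 0.91.

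**Step 3: simulation (80 patients, unstratified allocation, true HR 1, 40% node-positive).** With nodal HR 2-3, 10-30% risk and a 20-point or larger excess in one arm, the treatment-only HR is about 1.12-1.30, and stratifying returns it to 0.95-1.00. Repeat runs at 10-20% risk reached upper ends of 1.32 and 1.35. With nodal status as a covariate instead, at 25% risk and an excess of at least 17.5 points, the median HR falls from 1.14 to 0.97 (nodal HR 2) and from 1.26 to 1.00 (nodal HR 3).

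**Step 4: behaviour over all randomisations.** At 25% risk, rejection at true HR 1 is 4.0-4.1% treatment-only and 3.8-4.4% adjusted. The SD of the log HR is 0.478 against 0.483. At true HR 0.5, stratifying changes power by about −0.7 to +1.7 percentage points.

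**Step 5: comparison with sampling error.** The standard error of the log HR is about 2/√D for D events, so the 95% interval multiplies or divides the HR by exp(1.96 × 2/√D).
- 10% risk: D = 8, factor exp(1.386) = 4.0.
- 30% risk: D = 24, factor exp(0.800) = 2.2.
- A shift to 1.3 is ln 1.3 = 0.262 on the log scale. That is 0.262/0.707 = 0.37 of a standard error at 8 events and 0.262/0.408 = 0.64 at 24.
- Power for HR 0.5 is 16-40%. By Schoenfeld, 80% power needs 4(1.96 + 0.842)²/(ln 0.5)², which rounds up to 66 events.

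**The case against.** The strongest reply is that this is a choice of method on secondary end points in a trial sized for adverse events. Randomisation already makes a treatment-only test valid, the interval will be very wide whichever model is used, and stratification buys no overall precision. Even among trials with a 20-point imbalance and no true effect, the treatment-only test rejected only 5-7% of the time. All of this stands, and it limits the point to a cheap improvement. It does not show that a removable shift should be left in the one hazard ratio that will be reported.

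It is also fair that a dichotomy of N0 against N+ puts N1 and N3c together, and that node status needs a definition when some patients had neoadjuvant treatment. The first leaves some residual heterogeneity; the second has to be settled in the text. An objection that there are too few events to adjust has less force, because stratifying by one binary factor estimates no extra coefficient.

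A reader might infer three stronger things that the documents do not support:
- That the plan prescribes an unadjusted model. It does not use that word or say that treatment is the only term; it is silent on adjustment.
- That the type I error is inflated. Step 4 shows that it is not.
- That a spurious HR of 1.1-1.3 has a probability of 7-9%. That probability covers both directions; each arm has about half of it.

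**Conclusion.** The point holds as a conditional-bias and pre-specification issue on DFS and OS. No covariate, stratum or stratification factor is named, although nodal stage spans N0 to N3c and is known at entry. A 20-point or larger nodal imbalance is uncommon but not remote, and when it occurs a treatment-only estimate is displaced by up to about 30%; one nodal stratum removes that displacement. The displacement stays well within one standard error at the event counts considered, so it would rarely decide significance by itself. Every size quoted depends on the assumed nodal share, nodal HR and event risk, none of which the documents supply. The primary end point is unaffected.

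**What to change.** Add to the Statistical Analysis text that the DFS and OS hazard ratios and tests come from a Cox model stratified by one binary nodal factor, N0 vs N+, with the treatment-only model reported as a sensitivity analysis. Define the factor once, so that it applies in the same stated way to patients with and without neoadjuvant chemotherapy. If randomisation has not begun, stratify the allocation list by the same factor.

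The cost is a sentence or two and a definition, using data that eligibility screening already requires. The statistical downside is up to about 1 percentage point of power if only 5-8 events occur. The text should not claim a material gain in overall precision.
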